## 5. Study Treatment

Study patients will be recruited from those patients of the PI and IRB approved co-investigators who require bladder exstrophy closure as part of routine medical care.

Once patients have agreed to participate in standard bladder exstrophy closure surgery, patients will be approached with regard to interest in participation in the clinical study as per Section 4.5 above. Study patient will undergo a pre-operative non-contrast T1 and T2 weighted pelvic MRI (routinely obtained with standard clinical care) in order to plan pelvic osteotomies (also as per the standard of care).

### **Description of the specific medical/surgical procedures involved in the use of the investigational Device(s)**

On the day of scheduled surgery, the patient will undergo routine pelvic osteotomies, pelvic floor dissection, bladder closure, and abdominal wall closure as per the standard of care.

Some images from the preoperative MRI will be loaded onto a software program by certified/trained members of the IRB approved study team. These images will then be used to identify and highlight the exact location of the levator muscle fibers, rectum, urethra, bladder, and pelvic bones when mobilizing the bladder and prostatic plates as well as during pelvic floor dissection.

During the osteotomy, standard external fixation pins (orthopedic metal pins that are placed in the pelvic bones and protrude through the patient's skin) are placed by orthopedic surgeons as is per standard of care prior to the pelvic floor dissection. After placement of the external fixation pins, a sterile reference array will be attached to the external fixation pins by means of a VectorVision® 2-pin fixator. These 2-pin fixators are specifically designed to accommodate orthopaedic fixator pins that are routinely used in multiple orthopaedic procedures including pelvic osteotomies. The reference array communicates with the VectorVision® work station (placed in the operating room away from the patient table) by means of infrared light.

The VectorVision® software will be used to access the patient's preoperative MRI images. Four anatomical landmarks (i.e. pubic tubercles, anterior superior iliac spines, etc.) are used to register the patient's anatomy. These landmarks can be identified on MRI and visually by the surgeon in the operative field. This is accomplished by taking a sterile probe or instrument that is connected to the VectorVision® image guided system stylus and placing it directly on or near the landmarks on the patient. These landmarks are registered to the IGS work station. The virtual image or spaces of interest (i.e. pelvic floor and bladder) are now correlated to the surgical environment by collecting the 3D position of the pre-determined anatomic landmarks with a tracked pointer probe and relating them with the corresponding features extracted from the pre-operative MRI image sets.

The stereotactic imaging (which can be viewed in 3 dimensions) will be displayed on a monitor in the operating room in real time. The VectorVision® system has several sterile instruments and probes that can be used to visualize where the instrument is in real-time. This capability will allow for stereotactic imaging, confirmation that the anatomical structures of interest have been identified by both the surgeon's eyes in the operative field and the radiologist's eyes on the image monitor and thus allow for placement of the instruments during dissection of the pelvic floor.

Once the pelvic floor has been properly identified with stereotactic confirmation, the VectorVision® device will no longer be used. The reference array will be removed from the external fixation pins on the patient, and surgery will continue as it routinely does during standard clinical practice.

Postoperatively, the patient will receive routine clinical postoperative care which includes placement in traction and the use of an external fixator to prevent separation of the pubic bones as per standard of care. A suprapubic tube as well as ureteral stents is also left in place. Prophylactic antibiotics are continued post-operatively to prevent renal scarring from vesicoureteric reflux that is usually present and the hospital stay will be three to four weeks. Prior to discharge from the hospital the suprapubic tube will be removed and the patient will be schedule to follow up at routine clinical visits that typically occur at 2 weeks, 1 month, 3 months, 6 months, and 12 months after discharge from the hospital.

Outcomes, including success or failure of exstrophy closure, urinary continence, operative time, length of hospital stay, and a record of all peri-operative and post-operative complications, will be collected quarterly from the patient's medical record from all follow up visits for the 12 months following the surgical procedure.

No change in participant's care will occur if the study ends or the participant withdraws.

## **6. Inclusion/Exclusion Criteria**

### **6.1 Inclusion Criteria:**

- a. Age 0-7 years
- b. Diagnosis of classic bladder exstrophy
- c. Scheduled to undergo bladder exstrophy closure by the principal investigator at Johns Hopkins Hospital's Broadway campus.
- d. All eligible participants will be children whose parents or legally authorized representatives have already agreed and are being scheduled for osteotomy and bladder exstrophy closure as determined by their pediatric urologist.
- e. Parent or legally authorized representative who is, in the opinion of the investigator, reliable and willing to make themselves and patient available for the duration of the study.
- f. Parent or legally authorized representative is able to complete and sign the informed consent document.
- g. Patient judged by the investigator to have bladders of sufficient size and elasticity to be suitable for immediate closure as evidenced by the PI's assessment of the patient's bladder template [16].
- h. Patient with cardiopulmonary function sufficient to tolerate general anesthesia as evidenced by the pediatrician's and anesthesiologists assessment of the patient's overall cardio-pulmonary status.
- i. Patients requiring ferromagnetic metal objects such as a metal pace maker during the OR procedure.

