## 6.2 Exclusion Criteria

- a. Lack or withdrawal of consent for primary operative procedure.
- b. Parent or legally authorized representative who is, in the opinion of the investigator, not reliable or unwilling to make themselves and patient available for the duration of the study.
- c. Parent or legally authorized representative who is unable to understand, complete and/or sign the informed consent document. Non-English speaking parents will automatically be excluded if they are unable to read and understand the consent form.
- d. Patient who will not undergo osteotomy prior to closure for any reason

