## 11. Data and Safety Monitoring Plan

The research involves some risks to the participants. A group of designated faculty, that includes Pediatric Orthopedic Surgeon [name], Pediatric Anesthesiologist [name], and Adult Urologist [name] [name], will be involved in safety monitoring. These individuals will be notified promptly for any serious adverse events or deaths and will perform routine monitoring and oversight reviews of the research and postoperative outcomes to assess for trends or risks that were not previously identified. In the event of an adverse event, unanticipated problem, or a study deviation the IRB will be notified within 24-48 hours and the research will be halted pending review. Per the Johns Hopkins IRB policy 103.6b, "Unanticipated problems involving risks to participants or others" is defined as: The information is unexpected in terms of nature, severity, or frequency, given:

- a. The research procedures described in the protocol and informed consent document; and
- b. The characteristics of the subject population being studied; and
- c. The information indicates that participants or others are at greater risk of harm (including physical, psychological, economic, or social harm) than was previously known or recognized.

Also as per policy, the prompt reporting of unanticipated problems or events will occur as soon as possible after the PI learns of the event, but in all cases within 10 working days with the exception of death of a participant which must be reported within 3 working days.

Additionally, a team of designated faculty, including the PI's clinical fellow, the orthopedic surgeon ([name]), and the radiologist ([name]), will be present to monitor the patient during surgery. Standard safety monitoring by the anesthesiology team during surgery and post-operative nursing staff will monitor the patient for any safety concerns related to the surgery or immediate post-operative care.

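### Needing a ferromagnetic object is listed as an inclusion criterion in a study whose navigation depends on MRI, and no exclusion covers it

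*Combined protocol and SAP*

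**What the plan says.** Section 6.1 lists nine inclusion criteria, a to i. Items a to h are ordinary conditions that a child or parent must satisfy: age, diagnosis, scheduled surgery, agreement to osteotomy and closure, availability, consent, bladder template and fitness for anaesthesia. Item i, under the same heading, reads "Patients requiring ferromagnetic metal objects such as a metal pace maker during the OR procedure".

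Section 6.2 lists four exclusions, a to d. They cover consent to the operation, reliability of the parent, ability to understand and sign the consent form, and osteotomy; the last reads "Patient who will not undergo osteotomy prior to closure for any reason". None concerns metal, implants or MRI.

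Section 5 states "Study patient will undergo a pre-operative non-contrast T1 and T2 weighted pelvic MRI (routinely obtained with standard clinical care"). Its description of the device procedure says that landmarks touched with a tracked probe are used to register the patient by "relating them with the corresponding features extracted from the pre-operative MRI image sets".

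Section 11 says that after an adverse event, an unanticipated problem or a study deviation, "the IRB will be notified within 24-48 hours and the research will be halted pending review".

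**The concern.** Item i has the form of an exclusion but stands among the inclusions. Eligibility lists are applied as written by screening staff, monitors and the IRB, so its position matters.

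Three things are at stake. First, the population: followed literally, the rule shuts out nearly every child the study describes. Second, compliance: if the rule is ignored, most or all enrolments depart from a written criterion, and Section 11 attaches a serious consequence to deviations. Third, screening: if the item was meant to keep certain patients out, no criterion now does so.

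**Working it through.** No power, alpha or event count is involved, and the plan gives no figure to reproduce. The check sets the relevant texts side by side.

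| Source | What it establishes |
|---|---|
| Section 6.1, items a to h | Eight conventional conditions to be met |
| Section 6.1, item i | A ninth condition: the patient needs a ferromagnetic object, with a pacemaker as the example |
| Section 6.2, items a to d | Four exclusions, none on metal, implants or MRI |
| Section 5, Study Treatment | A pre-operative pelvic MRI for study patients |
| Section 5, device procedure | Navigation is registered to that MRI; intra-operative tracking is by infrared |
| Section 4.1 | 60 subjects aged 0-7 who need closure; no mention of ferromagnetic objects |

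**Step 1: literal eligibility.** If all of a to i must hold, a child who meets a to h but needs no ferromagnetic object fails 6.1. A child who meets a to h and has a pacemaker passes 6.1, and nothing in 6.2 removes that child.

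**Step 2: fit with the intervention.** Navigation as described cannot be delivered without the MRI. A ferromagnetic implant would ordinarily be expected to stand in the way of MRI. The documents do not say this, so it is an assumption from general knowledge.

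**Step 3: fit with the described population.** Sections 1 to 4 describe children who need exstrophy closure and give no reason to restrict the study to those needing ferromagnetic objects. Infrared tracking supplies no reason either. This mismatch does not depend on the assumption in Step 2.

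**Step 4: size.** Let k be the number of the 60 subjects who need such an object. The number ineligible as written is 60 − k. The documents do not give k.

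- k = 0: 60 − 0 = 60 ineligible.
- k = 60 (every subject counted as meeting item i): 60 − 60 = 0 ineligible.

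The second case requires item i to cover the metal used in every operation, a reading taken up under the objection. If item i refers to a patient-specific device such as a pacemaker, k should be at or near zero.

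**The case against.** The strongest reply is that this is a plain drafting slip that nobody would apply literally, with no bearing on any estimate. Four arguments support it.

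- **Timing.** Item i speaks of objects needed during the operation, whereas the MRI is done beforehand. The conflict with MRI therefore holds only for an object already in place at imaging. This is a fair qualification. The pacemaker example does suggest an implanted device, though, and an operation-only reading still gives no reason to require such objects.
- **Fixation pins.** Every subject receives "standard external fixation pins (orthopedic metal pins that are placed in the pelvic bones". If these are ferromagnetic and item i covers them, all subjects qualify. The documents do not say what the pins are made of. The pacemaker example points elsewhere, and on this reading item i would add nothing to item d, which already requires osteotomy. The reading is possible but strained.
- **Safety.** The MRI is described as routine care, so the study creates no new MRI exposure, and a child who could not be imaged could not be registered to the system. This stands: the documents show a missing screening criterion, not that patients would be harmed.
- **Deviations and halting.** The Section 11 consequence arises only if item i is enforced literally. This also stands as a condition on that part of the argument.

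It is also true that Section 6.1 never states that all items must be met; that is convention. The study is single-arm with descriptive analysis only (Sections 4.1 and 8.3), so no test or sample-size calculation is distorted. None of this makes the current eligibility rule usable. That the slip is easy to spot makes the correction easy; it does not supply the absent exclusion.

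**Conclusion.** The concern holds: item i is wrong as written. The eligibility rule contradicts both the population the protocol describes and the MRI-based procedure it requires. Up to 60 of 60 planned enrolments are ineligible on a literal reading, and no exclusion screens out children with ferromagnetic objects.

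The count rests on two assumptions: that all inclusion items must be met together, and that item i refers to a patient-specific device rather than the fixation pins. The MRI conflict further assumes that the object is in place at imaging and would be expected to preclude it. The misplacement itself needs neither of those last two assumptions. The likely practical harm is an unusable eligibility checklist and a missing screen, not a trial filled with such patients. Because this is an operative eligibility rule, it must be corrected.

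**What to change.** Remove item i from Section 6.1 and have the sponsor state what it was meant to do, reconciling Sections 5, 6.1 and 6.2. If the sponsor confirms that it was meant as an exclusion, as the MRI requirement implies, list it in Section 6.2 as item e. The revised wording should say whether it concerns objects present at the MRI, objects needed in the operating room, or both, and should make clear whether the fixation pins fall outside it. Check the screening checklist and consent form against the corrected lists; neither was available here, so whether they carry the same error is unknown.

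The cost is a short protocol amendment. The target of 60 does not change, since Section 8.3 bases it on yearly case numbers, and the descriptive analysis is untouched. Accrual from the population presumably intended should not be affected.

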## 6.2 Exclusion Criteria

- a. Lack or withdrawal of consent for primary operative procedure.
- b. Parent or legally authorized representative who is, in the opinion of the investigator, not reliable or unwilling to make themselves and patient available for the duration of the study.
- c. Parent or legally authorized representative who is unable to understand, complete and/or sign the informed consent document. Non-English speaking parents will automatically be excluded if they are unable to read and understand the consent form.
- d. Patient who will not undergo osteotomy prior to closure for any reason

## 7. Investigational Devices

### 7.1 Cranial Image Guided Surgery System

#### a. Common Classification

Name BrainLAB Cranial Image Guided Surgery System

#### b. Trade Names

VectorVision Cranial  
VectorVision ENT  
Kolibri cranial  
Kolibri ENT  
Cranial Essential  
Cranial Unlimited  
ENT Essential  
ENT Unlimited

c. Regulatory Class: Instrument/Stereotaxic; Regulatory Class II

d. Manufacturer: BrainLAB, AG

### 7.2 iPlan Cranial Software

#### a. Common/Classification

Name Planning System

b. Trade Names iPlan Cranial; iPlan Stereotaxy; iPlan ENT; iPlan Spine; iPlan View

c. Regulatory Class: Stereotactic Instrument; Regulatory Class II

d. Manufacturer: BrainLAB, AG

### 7.3 VectorVision® 2-pin Fixator

a. Manufacturer: BrainLAB, AG

## 8. Study Statistics

### 8.1 Primary Outcome Variables

Primary outcome variables include the amount of time added to the operative time, the closure complication (fistula, dehiscence, prolapsed) rate, the post-operative complication rate, the need for repeat surgeries, and the length of hospital stay.

## **8.2 Secondary Outcome Variables**

The secondary outcome for this trial is improved identification of the pelvic floor anatomy during bladder exstrophy closure as reported subjectively by the surgeon at the time of surgery.

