## **2. Objectives**

### **2.1. The primary objectives of this research are:**

- a. To determine the safety and efficacy of the use the Brainlab, Inc. VisionVector® Cranial Image Guided Surgery System during closure of bladder exstrophy.
- b. To verify the proper plane of dissection during closure of bladder exstrophy using the VisionVector® Cranial Image Guided Surgery System by visualizing in real-time where the surgeon's instruments are relative to the levator muscles and confirming that the bladder is being placed in the most posterior and inferior location possible.

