We propose to use this intraoperative stereotactic imaging system as a guide during the pelvic dissection in children ages 0-7 years that require closure of bladder exstrophy as we hypothesize that it will aid in identification and verification of the proper plane required for successful initial closure. Due to the nature of bladder exstrophy, this study cannot be done on adults. However, according to multiple studies, image guided surgery can be as safe and beneficial in the pediatric population as it has shown to be in adults [10-11]. We expect that, as seen with applications in other various fields, the use of image-guided surgery will allow for improved visualization and accurate navigation of the planned surgery [10, 12-13]. Additionally, the use of image-guided surgery should allow the possibility of extending the pelvic dissection safely in order to place the bladder in closer proximity to the puborectalis and levator ani muscles, allowing these muscles to aid in increasing bladder capacity postoperatively and ultimately increasing the rate of successful exstrophy closure and urinary continence [14]. We also expect that the use of image-guided surgery will result in a similar reduction in morbidity and mortality as well as a shortening of hospital stay.

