##### **a. Minimizing Bias**

Blinding is not applicable to this study design. The surgery and management of this procedure will be carried out exactly as in standard clinical practice with the exception of adding confirmatory intra-operative stereotactic imaging. As such, a placebo group or non-treatment group is not applicable to this study.

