#### **4.3. Study Outcomes**

##### **a. Primary Outcomes**

The primary outcomes for this trial are success or failure of exstrophy closure, urinary continence, operative time, length of hospital stay, and a record of all peri-operative and post-operative complications

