##### **b. Secondary Outcomes**

The secondary outcome for this trial is improved identification of the pelvic floor anatomy during bladder exstrophy closure as reported subjectively by the surgeon at the time of surgery.

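### Primary objective 2.1b has no primary outcome, and its only related measure is an unscaled surgeon report of improvement with no reading before guidance

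*Combined protocol and SAP*

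**What the plan says.** Section 2.1 gives two primary objectives. Objective (a) is "To determine the safety and efficacy of the use the Brainlab, Inc. VisionVector® Cranial Image Guided Surgery System during closure of bladder exstrophy". Objective (b) begins "To verify the proper plane of dissection during closure of bladder exstrophy" and goes on to confirming where the bladder is placed.

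The primary outcomes appear twice. Section 4.3.a reads "The primary outcomes for this trial are success or failure of exstrophy closure, urinary continence, operative time, length of hospital stay", followed by complications. Section 8.1 reads "Primary outcome variables include the amount of time added to the operative time, the closure complication (fistula, dehiscence, prolapsed) rate", followed by post-operative complications, repeat surgery and length of stay.

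The single secondary outcome is the same in 4.3.b and 8.2: "improved identification of the pelvic floor anatomy during bladder exstrophy closure as reported subjectively by the surgeon at the time of surgery".

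The trial is single arm (4.1) and blinding is declared not applicable (4.1.a). Section 8.3 plans descriptive statistics only, with an informal comparison against published rates. Section 5 says that the device is set aside once the pelvic floor has been identified with stereotactic confirmation. The outcome data listed in sections 5 and 11.5 do not include the surgeon's report.

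**The concern.** The word improved implies a comparison, and the plan supplies nothing to compare with. There is no control arm, no unaided reading within the case and no cited published rate of correct anatomical identification. A surgeon already in the right plane and a surgeon corrected by the display could both report good or improved identification, and the data would not tell them apart.

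The report is also the only recorded item that bears on 2.1b. If it cannot be interpreted, one of the two primary objectives ends without usable data. The unaided judgement cannot be reliably recovered after the operation, so the gap has to be closed before cases are done.

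**Working it through.** **Step 1. Map objectives to outcomes.**

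| Objective | Outcomes that address it | Status in the plan |
|---|---|---|
| 2.1a, safety and efficacy | Closure success or failure, continence, operative time, length of stay, complications, repeat surgery (4.3.a, 8.1) | Primary |
| 2.1b, plane of dissection | Surgeon's subjective report of improved identification (4.3.b, 8.2) | Secondary |
| 2.1b, bladder position | None listed | None |

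So 2.1a is covered. Objective 2.1b has no primary outcome, and half of it has no outcome at all.

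**Step 2. Look for a reference value for improved.**

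- Control arm: none (4.1).
- Unaided reading before the display is consulted: none specified in 4.3.b, 5 or 8.2.
- Scale or response categories: none specified.
- Published rate: 8.3 refers to published rates in general, but the protocol cites none for identification of the pelvic floor.
- Capture of the report: absent from the data lists in sections 5 and 11.5.

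**Step 3. Follow the workflow.** Under section 5 the device is used until identification is confirmed and is then removed. A case run to plan therefore ends in confirmed identification, whatever the surgeon had recognised unaided. That pushes the reported percentage towards its ceiling.

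**Step 4. What the percentage can and cannot say.** The plan has no figure of its own to reproduce here: the 60 in 8.3 rests on yearly case volume, with no alpha, power or effect size. As an illustration, take x reports of improvement in n = 60 and the exact (Clopper-Pearson) 95% interval:

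- lower limit = 0.025 quantile of Beta(x, n − x + 1)
- upper limit = 0.975 quantile of Beta(x + 1, n − x)

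Results:

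- x = 48: 48/60 = 80%, interval 67.7% to 89.2%.
- x = 60: 100%; the lower limit is 0.025^(1/60) = 0.940, so 94.0% to 100%.

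Section 4.2 also mentions 25 subjects enrolled. With 25 of 25 the lower limit is 0.025^(1/25) = 0.863, so 86.3% to 100%.

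These intervals describe how often surgeons say improved. Let b be the share of cases in which the plane was already identified unaided. The number that could truly improve is at most 60 × (1 − b). The documents give no value for b, so this bound runs from 60 (b = 0) to 0 (b = 1). A result of 60/60 is compatible with the whole range, and a larger sample would not narrow it.

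**Step 5. What a paired reading would give.** With a before and an after reading, change is counted directly. Illustrative counts: 3 of 60 changed gives 5%, interval 1.0% to 13.9%; 12 of 60 gives 20%, interval 10.8% to 32.3%. Agreement between surgeon and display is a second proportion with an interval of the same kind.

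**The case against.** Several points against the concern have force.

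- **Objective 2.1a is measured.** A reader might infer that the surgeon's report is the only measure of the primary objective. It is not. There are two primary objectives, and the lists in 4.3.a and 8.1 serve 2.1a. Closure success is also a secondary objective (2.2.a), but it is a natural efficacy measure for 2.1a, so its place among the primary outcomes is not an error.
- **To verify is not to improve.** Under 2.1b a surgeon already in the right plane is a successful verification. This stands, and it means that an outcome counting changes alone would also miss the objective. It does not rescue the present outcome, which is worded as improvement and records no agreement.
- **Checks exist in each case.** Section 5 has surgeon and radiologist both confirm the anatomy, 9.2 makes guidance a supplement to direct vision, and 9.5 has visible structures matched to the image. These are steps of the procedure; none is listed as recorded data.
- **Improvement can still be reported.** To say that it cannot be measured would go too far, because a surgeon can record a perceived change. What is missing is a reference or check for it. Nor do the documents say that the report is made only once, or after the display has been seen; they say only that it is made at the time of surgery.
- **A form may exist elsewhere.** Section 11.6 mentions case report forms and the contents list mentions appendices. The point is therefore that the protocol text does not specify a reading, not that none exists.
- **This is a descriptive pilot.** True, but a description also needs a defined quantity.

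**Conclusion.** The concern holds for objective 2.1b. That objective has no primary outcome, and its only related measure has no specified scale, unaided reading or reference rate. The resulting percentage cannot be read as a change due to the display, and the workflow in section 5 drives it upwards in any case.

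The size is best stated without assuming how good the surgeon is: a report of improvement in all 60 cases would look precise (94.0% to 100%) and yet leave the number of true improvements anywhere from 0 to 60. Closure by the principal investigator (6.1.c) at a centre that section 10 describes as the world's leading one makes it tempting to say that only a few cases could improve. The documents give no rate of correct unaided identification, so no such number is supported.

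The verdict rests on the protocol text as supplied. A form that already records an unaided reading would reduce the problem to one of documentation.

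A separate, smaller matter is that Background says guidance "should allow the possibility of extending the pelvic dissection safely", while 4.1.a says the surgery and management will be "carried out exactly as in standard clinical practice" apart from confirmatory imaging. One is an expectation and the other a statement of procedure, so they are in tension. They must be reconciled; which should prevail is not a statistical question.

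**What to change.** In 4.3 and 8.2, define a paired measure:

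1. Before consulting the display, the surgeon records on a fixed scale whether the pelvic floor and levator plane are identified, and with what certainty.
2. After consulting it, the surgeon records the same rating, whether the display agreed with the direct view, and whether the dissection was changed.
3. Report two proportions, each with an exact 95% interval: cases with agreement between surgeon and display (verification), and cases with a changed rating or plane (improvement).
4. Name these as the outcome for objective 2.1b, and add them to the data collected under sections 5 and 11.5.

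Reconcile Background with 4.1.a on whether guidance may alter the dissection.

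The cost is a short form, about a minute per case, and wording changes. No control arm, extra assessor, visit or formal test is needed, so the descriptive plan in 8.3 can stay. Two limits remain and should be stated in the protocol: the rating is still subjective and unblinded, and it does not measure bladder position, the other half of 2.1b.
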